6.10.2.1.1 Descriptive Summaries

Descriptive statistics for the total comfort score and the 14 day average comfort score will be presented along with the number and percentage of patients at each comfort classification will be presented for each treatment group for Days 1 to 14, Days 15 to 28, Days 29 to 42 and Days 43 to 56 for the recorded eye. The percentage will be out of the number of patients at each timepoint who had some data and therefore the total score could be calculated.

The percentage of missing data points will be summarised for each treatment group for Days 1 to 14, Days 15 to 28, Days 29 to 42 and Days 43 to 56.

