6.9.2 Patient diary card

All patients will be issued with a diary card and will be asked to score comfort on a scale of 0 to 4 as shown in Table 5 below. The patient may make further comments (e.g. a difference in comfort between the two eyes) in the diary card.

| | Table 5 | Eye comfort scoring |
|--|---------|---------------------|
|--|---------|---------------------|

| Score | Description |
|-------|---|
| 0 | Perfectly comfortable |
| 1 | Slight discomfort. Aware of some burning, itching or stinging for up to half a minute after using the eye drop, solution but the discomfort improves without treatment. |
| 2 | Moderate discomfort. Burning, itching or stinging lasts for half a minute or longer but improves without treatment. |
| 3 | Severe discomfort. Burning, itching or stinging last for at least half a minute and requires washing the eyes to relieve it. |
| 4 | Unbearable burning itching or stinging. So severe that you cannot continue treatment. |

Scoring will be carried out at 0.5, 1, 2, 3 and 5 minutes after instillation of the drops and, in addition, patients will be asked to insert a brief description (up to 5 words) of how the eyes feel at the 3-minute time point. A list of suggested descriptor words will be provided but patients will be free to use any terminology they wish. Suggested descriptors are:

- Normal, cool, comfortable, smooth, fresh
- Uncomfortable, gritty, dry, sticky
- Burning, itchy, stinging, painful

In addition, there will be space for any other comments the patient may have.

Diary cards will be checked by the trial nurse or the PI/blind assessor at each visit to ensure that they are being filled in correctly and regularly.

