6.2 General Derivations

This section provides details of general derivations. Detailed descriptions of specific parameter derivations are provided later in the SAP.

• Definition of baseline

The Baseline value will be defined as the pre-dose value on Day 1, if that is missing or the first administration is not on Day 1, it will be defined from the most recent value available and recorded prior to the first administration of study treatment.

Incomplete dates

For calculation purposes, incomplete dates will be completed using worst case, the most conservative value possible. For example, if the start date has a missing day value, the first day of the month will be imputed for study day computations. If day is

missing for an end date, the last day of the month will be imputed. Similar logic will be assumed for missing month and year components.

• Methods for handling withdrawals and missing data

There will be no imputation of missing data. Screening data will be used if baseline is missing.

Statistical testing and graphical presentations will not be carried out for any given score or measurement if there are less than 5 results, for either the placebo or active group, for that score or measurement at any single time point.

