6.10.2 Secondary Endpoints

6.10.2.1 Post-instillation comfort

Post-instillation comfort scores will only be available for the least comfortable eye. The eye that the scoring was recorded on will not be captured on the eCRF.

A score of 0 to 4 will be recorded at 0.5 min, 1 min, 2 min, 3 min and 5 min each morning and evening on diary card.

The total score over two-week periods for days 1 to 14, 15 to 28, 29 to 42 and 43 to 56 will be calculated for each patient by summing the scores from the five timepoints taken each morning and evening over the 14 days, therefore the total score will have a possible range of 0 to 560. If there are 20 or more missing data points during the period, then the total score will not be calculated and set to missing.

For derived non-missing scores, an average score for the period will also be calculated as follows:

$$Average \ score = \frac{Total \ score}{Number \ of \ non - missing \ days}$$

The average score at each two week-period will be classified as follows: an average total comfort score of < 10 will be deemed to be comfortable/acceptable, 10 - 19 will be moderately uncomfortable, 20 - 29 will be very uncomfortable and ≥ 30 will be severely/unacceptably uncomfortable.

The number and percentage of missing data over the two-week period will be calculated, where 140 data points would expected to be recorded over 14 day period.

Should the five scores not be available at any morning or evening timepoint there will be no imputation, and the total score and classification will be derived for the two-week period for that patient regardless of missing data.

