6.10.2.1.2 Analysis

The classification of the average daily post-instillation comfort score will be analysed using an ordinal logistic regression model. The model will include treatment and visit as fixed effects and a treatment-by-visit interaction.

The following variance/covariance matrix structures for the repeated visits by a patient will be assessed: Compound symmetry, 1st order autoregressive, Toeplitz and unstructured. The variance/covariance matrix structure that results in the smallest Akaike information criterion (AIC), indicating the best model fit will be selected.

Assumptions about the proportionality of odds will also be assessed by appropriate methods such as by fitting fixed and random effects at each partition and testing the equality of the effects at different partitions. Should assumptions not hold, then the treatment odds ratios for the individual cumulative levels of the variable will be presented.

The adjusted least squares (LS) estimate for the treatment odds ratio (nomacopan:Placebo) along with corresponding 95% CI will be presented for each treatment period.

A null hypothesis of no change in classification of total post-instillation comfort score at Days 43 to 56 between treatment groups (nomacopan/Placebo) will be assessed and a p-value will also be reported.

The extent of missing data will be taken into consideration when analysing the total score data. Should it be felt appropriate, alternative analysis may be carried out and/or

sensitivity analyses using imputation methods such as last observation carried forward will also be considered.

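### Most patients who stop the drops because of discomfort will have no Days 43 to 56 comfort score, and no SAP rule places them in the worst comfort class

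*SAP*

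**What the plan says.** Protocol 6.9.2 has patients score comfort from 0 to 4 at five times between half a minute and 5 minutes after the drops. Table 5 there defines score 4 as "Unbearable burning itching or stinging. So severe that you cannot continue treatment".

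SAP 6.10.2.1 sums the scores over each two-week period, divides by the number of days with data, and sorts the average into four classes, from below 10 up to 30 or more. It gives two rules for incomplete diaries:

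- "If there are 20 or more missing data points during the period, then the total score will not be calculated and set to missing".
- When some of the five scores are absent at a session, "the total score and classification will be derived for the two-week period for that patient regardless of missing data".

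SAP 6.2 states the general rule: "There will be no imputation of missing data". SAP 6.10.2.1.1 takes class percentages "out of the number of patients at each timepoint who had some data and therefore the total score could be calculated". SAP 6.10.2.1.2 fits a repeated-visit ordinal model, with an odds ratio for every period but a p-value for one only: "A null hypothesis of no change in classification of total post-instillation comfort score at Days 43 to 56". Last observation carried forward (LOCF) is mentioned there as something to be considered.

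**The concern.** On this scale the worst outcome is itself a reason for the data to stop. A patient who gives up the drops because they sting produces no further scores, and no sentence in the SAP assigns that patient a class. The missingness is informative: the comparison in later periods is made among patients who tolerated the drops.

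Tolerability is part of the primary objective (Protocol 5.1, SAP 2.1), and post-instillation comfort is the endpoint that measures it most directly. If more patients stop for discomfort on one arm, that arm's comfort table does not show it.

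The documents make the scenario plausible without giving a rate. This is the first study by the ocular route (Protocol 3.4). The Amendment 5 justification records that stinging from ciclosporin drops leads some patients not to use them. Protocol 8.2.1 foresees patients stopping the product because of adverse events that they find intolerable.

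**Working it through.** **The SAP's own figures.** Five readings × 2 doses × 14 days = 140, which agrees with "where 140 data points would expected to be recorded over 14 day period". Then 140 × 4 = 560, which agrees with "therefore the total score will have a possible range of 0 to 560". Each day has 10 readings, so the highest daily average is 10 × 4 = 40.

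**The 20-point rule in doses.** Each dose carries 5 readings, so 20 missing points is 4 doses, or 2 days. Assume complete diaries up to stopping. A last scored dose on the evening of Day 12 leaves 2 × 10 = 20 points missing, and the Days 1 to 14 total is set to missing. A last scored dose on the morning of Day 13 leaves 15 missing, and the total is calculated. The same pattern repeats in each period:

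| Last scored dose | Possible last doses | Periods with a value |
|---|---|---|
| Day 1 morning to Day 12 evening | 24 | none |
| Day 13 morning to Day 26 evening | 28 | Days 1–14 |
| Day 27 morning to Day 40 evening | 28 | first two |
| Day 41 morning to Day 54 evening | 28 | first three |
| Day 55 morning to Day 56 morning | 3 | all four |

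Of the 111 possible premature last doses, 24 + 28 + 28 + 28 = 108 leave no value in the tested period, and 24 leave no value anywhere.

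**The other rule.** Suppose totals are derived whatever is missing, and a day with any reading counts as a day. A patient who stops before Day 43 still has no Days 43 to 56 value. In the stopping period the final scores can be diluted:

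- Ten days at 0, then all 4s at the Day 11 morning dose: total 5 × 4 = 20, average 20/11 = 1.8, the most comfortable class.
- All 4s at the very first dose, then stopping: 20/1 = 20, the second-worst class.
- All 4s at both Day 1 doses, then stopping: 40/1 = 40, the worst class.

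So this rule sometimes classes the patient as worst in the stopping period, but not dependably, and never carries the class into later periods.

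**Illustration (assumed stopping pattern; 8 per arm from 16 randomised 1:1).** Let k active patients stop early for stinging, with everyone else comfortable.

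| k | Days 43–56 as planned | Stops counted | Difference | Fisher p, two-sided |
|---|---|---|---|---|
| 1 | 0/7 vs 0/8 | 1/8 vs 0/8 | 12.5 points | 1.00 |
| 2 | 0/6 vs 0/8 | 2/8 vs 0/8 | 25 points | 0.47 |
| 3 | 0/5 vs 0/8 | 3/8 vs 0/8 | 37.5 points | 0.20 |
| 4 | 0/4 vs 0/8 | 4/8 vs 0/8 | 50 points | 0.077 |

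As planned, the difference is 0 points in every row. At k = 4 only 4 active results remain, so the SAP 6.2 minimum of 5 results per group also cancels the test and the graphs.

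**The case against.** A reader might infer that the comfort endpoint omits every patient who could not tolerate the drops. It does not. Periods completed before stopping stay in the summaries and can be used by the repeated-visit model. Complete omission needs a last scored dose by the evening of Day 12, and then only under the 20-point rule.

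A reader might also infer that the worst class is out of reach for anyone still dosing. Table 5 does not support that. Score 3 is severe discomfort relieved by washing the eyes, with no mention of stopping, and constant 3s give 10 × 3 = 30, which is already the worst class.

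Nor can LOCF be dismissed outright. SAP 6.10.2.1.2 does not say at what level it would apply. Carrying single readings forward would take final 4s into every later period. Carrying period classes forward would usually bring an earlier, possibly more comfortable class, and would bring nothing for a stop by Day 12. What stands is that LOCF is optional and its level is unspecified.

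The strongest point is that intolerance is reported elsewhere: reasons for stopping treatment (SAP 6.5), the percentage of missing comfort points by arm and period (6.10.2.1.1), diary listings (6.10.2.1.3) and adverse events leading to discontinuation (6.14.1.2). A table of 0/6 versus 0/8 would therefore sit in the same report as two discontinuations. The primary endpoint, ocular treatment-emergent adverse events, is separate. Comfort is one of five secondary endpoints, without multiplicity adjustment, in an unpowered study (Protocol 11.5), and the rabbit irritation results in Protocol 3.2.1 were mild. All of this limits the harm; none of it gives the stopped patient a comfort class.

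**Conclusion.** The gap is real and confined to the comfort endpoint. As written, nearly all early stops for discomfort leave no value in the one tested period, and neither missing-data sentence reliably puts such a patient in the worst class. In the illustration, two such stops on active turn a 25-point difference into 0. That rests on an assumed stopping pattern, since the documents give no rate, and on complete diaries up to the stop. With Fisher p = 0.47 for two stops, the consequence is for the description of tolerability rather than for a significance claim. The documents do not support a claim that intolerance is hidden from the report. This is a worthwhile, low-cost improvement to a tolerability endpoint. The contradiction within SAP 6.10.2.1 needs resolving in any case.

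**What to change.** In SAP 6.10.2.1, before unmasking:

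1. Reconcile the two missing-data sentences so that one rule governs incomplete periods.
2. State that a patient who permanently stops the drops because of post-instillation discomfort is placed in the worst comfort class for the stopping period and every later period, and stays in the percentage denominator and the ordinal model. Identify these patients from the recorded stopping reason, supported by adverse event terms and the last diary scores.
3. Leave stops for any other reason as missing. This includes ocular adverse events without instillation discomfort, such as worsening of the underlying disease; otherwise a patient whose disease worsened would be counted as unable to tolerate the drops.
4. Show the number and day of discomfort stops by arm beside the comfort table.

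The cost is mainly SAP wording plus some masked judgement on the stopping reason, because the documents do not show whether the CRF separates post-instillation discomfort from other reasons. The comfort result may look less favourable for the active arm.

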6.10.2.1.2 Analysis

The classification of the average daily post-instillation comfort score will be analysed using an ordinal logistic regression model. The model will include treatment and visit as fixed effects and a treatment-by-visit interaction.

The following variance/covariance matrix structures for the repeated visits by a patient will be assessed: Compound symmetry, 1st order autoregressive, Toeplitz and unstructured. The variance/covariance matrix structure that results in the smallest Akaike information criterion (AIC), indicating the best model fit will be selected.

Assumptions about the proportionality of odds will also be assessed by appropriate methods such as by fitting fixed and random effects at each partition and testing the equality of the effects at different partitions. Should assumptions not hold, then the treatment odds ratios for the individual cumulative levels of the variable will be presented.

The adjusted least squares (LS) estimate for the treatment odds ratio (nomacopan:Placebo) along with corresponding 95% CI will be presented for each treatment period.

A null hypothesis of no change in classification of total post-instillation comfort score at Days 43 to 56 between treatment groups (nomacopan/Placebo) will be assessed and a p-value will also be reported.

The extent of missing data will be taken into consideration when analysing the total score data. Should it be felt appropriate, alternative analysis may be carried out and/or

sensitivity analyses using imputation methods such as last observation carried forward will also be considered.

6.10.2.1.3 Listing

All post-instillation comfort diary card data will be listed.

6.10.2.2 Visual acuity by Early Treatment Diabetic Retinopathy Study (ETDRS) charts

6.10.2.2.1 Descriptive Summaries

Descriptive statistics for observed and change from baseline (Day 1) number of ETDRS letters will be presented for each treatment group at each visit for right eye, left eye and the score from worse of the two eyes at the visit. The worst eye is determined from the eye assessed on the clinical scoring CRF page at the same visit. The number and percentage of patients whose assessed eye differed from the previous assessment will be presented.

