6.9 Safety and Efficacy Assessments

Safety will be assessed by the Investigator from history and clinical examination. Adverse events (AE) will be recorded in the CRFs and in part 2 of the study, a comparison will be made between the number, type and severity of AEs between the treatment groups.

Comfort will be assessed on the basis of the patient diary cards. A comparison of the total comfort scores between the randomised treatment groups in part 2 of the study, will be made at the conclusion of the trial. For each treatment group a total comfort score of < 10 will be deemed to be comfortable/acceptable, 10 - 19 will be moderately uncomfortable, 20 - 29 will be very uncomfortable and > 30 will be severely/unacceptably uncomfortable.

Composite eye sign and symptom scoring will be carried out by the investigator/blind assessor (depending on the part of the study) at each scheduled clinic visit. Symptoms will be scored by the patient in response to specific questioning by the investigator/blind assessor. Signs will be scored by the investigator/blind assessor as a result of the clinical examination. At each visit the patient will be asked which eye feels to be the worst affected at the time of the visit and that eye will be used for the examination. If both eyes seem to the patient to be equally affected the right eye will always be used. The worst affected eye may change from visit to visit.

For each sign/symptom a numerical score 0 - 3 will be awarded (see table in Section 17.1 (AKC and VKC) and 17.2 (severe allergic conjunctivitis - SAC or PAC). These scores will be summed at the conclusion of the examination and this will be known as the composite score. The minimum possible composite score is 0, the maximum 33 (AKC and VKC) or 27 (severe allergic conjunctivitis (SAC or PAC)). All statistical comparisons, in part 2 of the study, will be done on the basis of the composite score for each patient/visit.

MMP-9 detection using the *Inflammadry*[®] device. This device will give a binary (positive/negative) result which will be recorded in the CRFs at each time point and a comparison of the numbers of positives in each randomised treatment group will be made.

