6.10.2.2.2 Analysis

Change from baseline (Day 1) for the ETDRS on the worst eye at Day 14, Day 28, Day 42 and Day 56 will be analysed using a mixed-effect model for repeated measures. The model will include baseline ETDRS as a covariate, treatment group and visit as fixed factors and the treatment-by-visit interaction.

The variance/covariance matrix structure that results in best model fit will be selected using the process described in section 6.10.2.1.2.

Assumptions of normality will be assessed visually using diagnostic plots. Should assumptions of normality not hold, transformations such as percentage change and ratio to baseline will be considered. If there remains uncertainty regarding the assumptions, a non-parametric analysis may be considered as an alternative.

The LS means and 95% confidence interval will be presented for each visit and treatment. The adjusted LS mean difference (nomacopan - placebo) and 95% confidence interval will be presented for each visit.

A null hypothesis of no change in ETDRS at Day 56 between treatment groups (nomacopan - placebo) will be assessed and a p-value will also be reported.

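### Visual acuity change from Day 1 can compare two different eyes, because the SAP re-selects the analysed eye at every visit

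*SAP*

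**What the plan says.** SAP 6.10.2.2.1 summarises letters for the right eye, the left eye and the worse eye, and defines the last of these by reference to another assessment: "The worst eye is determined from the eye assessed on the clinical scoring CRF page at the same visit". Under Protocol 6.9 and 6.9.1, and SAP 6.10.2.3, the clinically scored eye is the one the patient calls worst affected at that visit. Acuity plays no part. Protocol 6.9 adds "The worst affected eye may change from visit to visit" and, for ties, "If both eyes seem to the patient to be equally affected the right eye will always be used".

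The model in SAP 6.10.2.2.2 takes "Change from baseline (Day 1) for the ETDRS on the worst eye" at Days 14, 28, 42 and 56, with a p-value at Day 56. On baseline it says "The model will include baseline ETDRS as a covariate". The general rules in SAP 6.2 are "The Baseline value will be defined as the pre-dose value on Day 1" and "Screening data will be used if baseline is missing". Neither says which eye the baseline comes from.

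The SAP does foresee switching: "The number and percentage of patients whose assessed eye differed from the previous assessment will be presented".

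**The concern.** A change score is meant to follow one eye over time. Here the eye is chosen again at each visit, after treatment has started, on how it feels and not on acuity. If the eye scored at Day 56 is not the one scored at Day 1, the modelled change contains the fixed difference between that patient's two eyes as well as any real change. That adds noise.

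It also lets treatment influence which eye is analysed. Drops go into both eyes and ties go to the right eye. A patient scored on the left at Day 1 whose eyes later feel alike is therefore moved to the right eye. The documents give no evidence that this will happen more in one arm, but nothing in the rule prevents it.

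At stake is the reading of one secondary endpoint: the worst-eye series is the only acuity variable that is modelled and tested.

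**Working it through.** **Tracing the rule.** There is no planned figure to reproduce, since SAP section 3 sets the sample size on practical grounds.

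1. Clinical scoring and ETDRS are both scheduled at Day 1 (Protocol 17.3), so the same-visit rule yields a Day 1 eye.
2. At each later visit the rule yields that visit's scored eye.
3. The model has a single baseline covariate, and no text matches it to the later eye.

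Example with assumed letters: right 80 and left 65 at both visits, right scored at Day 1 and left at Day 56. The rule gives 65 − 80 = −15. Same-eye change is 0 in either eye. With 8 per arm, this one patient moves the arm mean by 15/8 = 1.875 letters.

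**Does the planned switch count reveal the problem?** It compares with the previous assessment, not with Day 1.

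| Scored eye at Days 1, 14, 28, 42, 56 | Visits flagged | Visits where the change crosses eyes |
|---|---|---|
| R, L, L, L, L | 14 | 14, 28, 42, 56 |
| R, L, R, R, R | 14, 28 | 14 |

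**Precision.** All inputs are assumptions. Retest SD is 5 letters per reading; d is the SD of the between-eye difference (5 to 15, mean zero); p is the share on a different eye from Day 1; h is the SD of true change between patients.

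Var(change) = 2 × 5² + h² + p × d²

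SD of change in letters:

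| p | h | d = 5 | d = 10 | d = 15 |
|---|---|---|---|---|
| 0 | 0 | 7.07 | 7.07 | 7.07 |
| 5% | 0 | 7.16 | 7.42 | 7.83 |
| 10% | 0 | 7.25 | 7.75 | 8.51 |
| 25% | 0 | 7.50 | 8.66 | 10.31 |
| 40% | 0 | 7.75 | 9.49 | 11.83 |
| 0 | 8 | 10.68 | 10.68 | 10.68 |
| 5% | 8 | 10.74 | 10.91 | 11.19 |
| 40% | 8 | 11.14 | 12.41 | 14.28 |

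For example, p = 40%, d = 15, h = 0 gives √(50 + 0.40 × 225) = 11.83. The standard error of the arm difference is SD × √(2/8) = 0.5 × SD. With h = 0 that is 3.54 with no switching and 3.58 to 5.92 with switching.

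**Bias and type I error.** These come from simulation: 20,000 trials per cell, 8 per arm, between-patient SD 12, and ANCOVA of Day 56 change on baseline. This is a single-visit simplification of the repeated-measures model. If the other eye reads m letters better on average, bias = (difference in switching between arms) × m.

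| Switching | m | Bias (letters) | Type I error as written |
|---|---|---|---|
| Equal, random | 0 | 0 | 4.4–5.2% |
| 10% v 25% | 5 | 0.15 × 5 = 0.75 | 4.6–5.3% |
| 10% v 25% | 10 | 0.15 × 10 = 1.5 | 4.9–6.0% |
| 10% v 40% | 0 | 0 | 4.6–5.2% |
| 10% v 40% | 5 | 0.30 × 5 = 1.5 | 5.1–6.6% |
| 10% v 40% | 10 | 0.30 × 10 = 3.0 | 6.2–9.8% |

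With the Day 1 eye fixed, bias in the unequal-switching cells is under 0.1 letters and type I error is 4.6–5.3%.

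**Power.** For an assumed 5-letter effect with h = 8, a fixed eye gives 13.6–14.2%. As written, power is 14.0%, 13.7%, 12.1% and 10.0% for (d, p) = (5, 5%), (5, 10%), (10, 25%) and (15, 40%). A larger assumed effect shows the loss more clearly. For 10 letters, a same-eye SD of change of 8, and 25% switched with a 10-letter gap in random direction, the SD becomes √(64 + 0.25 × 100) = 9.43. Power then falls from 0.71 to 0.56 (normal approximation).

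**The case against.** **The baseline could be eye-matched.** The SAP plans right-eye and left-eye changes, so the scored eye's own Day 1 value could be subtracted, and a repeated-measures model can take a covariate that varies by visit. That reading is possible, but it is written nowhere and sits badly with a single baseline covariate. On either reading, a rule is missing.

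**The test may be sound.** Under equal switching, or with no systematic difference between the eyes, type I error stays near 5%. This stands. The fault is that the result is not a same-eye change; the test is not generally invalid. The inflated figures need strongly unequal switching, about 1 against 3 of 8 patients, together with a large average gap between the eyes.

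**Switching may be rare.** Ties go to the right eye, and Protocol 2.1 says the eyes are usually affected equally. This also stands, although that statement concerns disease and not acuity.

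**Safeguards exist.** Right-eye and left-eye summaries remain valid same-eye results. The listings (SAP 6.10.2.2.3 and 6.10.2.3) and the display by patient in SAP 6.10.4 let a reader reconstruct most crossings. None of this changes the variable that is modelled and tested.

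**Following the worst eye is deliberate.** That is so for the composite score, where only one eye is scored. Acuity is available for both eyes, so the constraint does not carry over.

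**Conclusion.** The concern holds. Followed as written, the acuity model mixes eyes for every patient whose scored eye differs from the Day 1 eye, and the planned switch count does not identify those patients. This rests on reading the same-visit rule as applying at Day 1 too, which is the natural reading but not an express statement.

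The size is unknown. Under the stated assumptions, the loss of precision runs from negligible at 5% switching to substantial at 40% with a large between-eye difference. Bias needs unequal switching and a systematic gap between the eyes. Protocol 11.5 says the trial is not powered for its primary analysis and that no single significant finding will be given undue weight. The case therefore rests more on interpretability than on power or error rate. The change should be made, but the trial's main conclusions do not depend on it.

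**What to change.** Amend SAP 6.10.2.2.2 before unmasking:

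- Define the acuity study eye as the eye clinically scored at Day 1, or at screening if Day 1 is missing, in line with SAP 6.2.
- Use that eye's letters for the baseline covariate and for every later visit. The choice then precedes the first dose, so treatment cannot affect it.
- Keep the right-eye, left-eye and existing switch summaries. Add, by visit and arm, the number of patients whose scored eye differs from the Day 1 eye.
- Leave the composite score as designed.

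A smaller alternative is to keep the eye scored at each visit and state that its own Day 1 value is the baseline. That removes the cross-eye subtraction, but the eye is still chosen after treatment starts and the baseline varies by visit.

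The cost is a few lines of SAP text and one extra count. No new data are needed: both eyes' acuity is already summarised and listed, and the scored eye is captured on the eCRF. The downside is that the acuity eye may differ from the eye clinically scored at a later visit.
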